4.3.3 Sensitivity analysis

The following sensitivity analyses will be performed targeting the same estimand as the primary estimand to assess the impact of the missing data handling strategy.

Pattern mixture model with copy increment from placebo after WOCF

After using the WOCF approach to impute data after taking the select prohibited/rescue medications and to impute missing data for participants who discontinue study intervention due to lack of efficacy (as described for the primary analysis), the primary endpoint will be analyzed with imputed missing Week 24 values using a pattern mixture model with copy increment from placebo (1). This copy increment from placebo implies that when participants discontinue intervention early, they continue to take advantage of their previous therapy, but they progress in the same way as participants in the placebo group.

The imputed dataset will be analyzed by fitting an ANCOVA model with same covariates as the primary analysis. Descriptive statistics including number of participants, mean, standard error, and least squares (LS) means will be reported. In addition, difference in LS means and the corresponding 95% confidence intervals (CI) will be reported along with the p-values.

Tipping point analysis for missing data

After using the WOCF approach to impute data after taking select prohibited/rescue medications and to impute missing data for participants who discontinue study intervention due to lack of efficacy (as described for the primary analysis), a tipping point analysis will be performed for the primary endpoint with imputed missing Week 24 values as follows:

- **Step 1.** Monotone missing pattern will be induced by Markov Chain Monte Carlo (MCMC) method using PROC MI: for participants who have intermediate missing values, the intermediate missing values will be imputed assuming a multivariate normal distribution over observations from all visits. 40 datasets with a monotone missing pattern will be obtained using this method.
- **Step 2.** For each of the imputed dataset with monotone missing pattern obtained in Step 1, the remaining missing data will be imputed using the regression method for the monotone pattern with adjustment for covariates including response variable, intervention groups, angioedema at baseline, region, and baseline value of the corresponding endpoint. All available data in the monotone missing pattern data will be used. One imputed dataset will be obtained for each of the imputed dataset at Step 1. So, 40 fully imputed datasets will be obtained altogether.
- **Step 3.** The imputed values in dupilumab group are added by a positive amount d for each imputed data set.
- **Step 4.** The imputed values in placebo group are subtracted by a positive amount p for each imputed data set.
- **Step 5.** Change from baseline in endpoint will be analyzed using ANCOVA model same as the one in primary analysis. Then the SAS MIANALYZE procedure will be used to generate statistical inferences by combining results from the 40 analyses using Rubin's formula.

Step 3 to Step 5 will be repeated iteratively until the p-value for treatment effect of dupilumab compared to placebo estimated in Step 5 is >0.021 at IA or >0.043 at final analysis.

LS mean difference between dupilumab and placebo in change from baseline in primary endpoint at Week 24 and the corresponding p-values will be provided for each combination of shift parameters.

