Within each study, Study A and Study C (omalizumab naïve) and Study B (omalizumab intolerant or incomplete responders), the multiplicity procedure is proposed to control the overall Type-I error rate for testing the primary endpoint and the key secondary endpoints. Detailed hierarchical testing procedure will be defined in each study SAP.

Study A and Study C are each considered positive when the primary endpoint achieves statistical significance with 2-sided significance level 0.05 for that study.

For study B, an interim analysis will be performed using the O'Brien-Fleming approach with information fraction 0.77 and overall type-I error controlled at 0.05, the alpha spending at this interim analysis will be 0.021, and the alpha spending at the final analyses when all 104 participants complete the study will be 0.043. The decision process that applies to this interim analysis is outlined in [Section 9.5](#).

Multiplicity adjustment for the other efficacy endpoints will be described in the study SAP.

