## 9.5 INTERIM ANALYSES

The database locks will be implemented separately for Study A (omalizumab naïve), Study B (omalizumab intolerant or incomplete responders), and Study C (omalizumab naïve).

No interim analysis is planned for Study A and Study C.

For each Study A and Study C, a primary database lock will be performed when all randomized participants have completed their treatment phase. Final analyses in the CSR will be based on all data collected up to this database lock. The database will be updated at the end of the study for all participants to include the post-treatment follow-up information and updates for the events previously ongoing at the time of the primary lock. Additional data between this database lock and last participant completing last visit will be summarized in a CSR addendum.

For Study B, an interim analysis (IA) will be performed when the first 80 randomized participants would have completed their 24-week treatment period by the interim analysis cut-off date. This interim analysis will use the O'Brien-Fleming approach with information fraction 0.77 and overall type-I error controlled at 0.05, with an alpha spending at the interim analysis of 0.021, and an alpha spending at the final analysis (when all 104 participants complete the study) of 0.043.

The possible outcomes from this interim analysis are summarized below and in [Table 9](#):

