The imputed dataset will be analyzed by fitting an ANCOVA model same as the one in primary analysis. Descriptive statistics including number of participants, mean, standard error, and least squares (LS) means will be provided. In addition, difference in LS means and the corresponding 95% confidence intervals (CI) will be provided along with the p-values.

Tipping point analysis

After using the WOCF approach to impute data after taking select prohibited/rescue medications and to impute missing data for participants who discontinue treatment due to lack of efficacy (as described for the primary analysis), a tipping point analysis will be performed for the primary endpoint with imputed missing Week 24 values as follows:

- **Step 1.** Monotone missing pattern will be induced by Markov Chain Monte Carlo (MCMC) method using PROC MI: for participants who have intermediate missing values, the intermediate missing values will be imputed assuming a multivariate normal distribution over observations from all visits. 40 datasets with a monotone missing pattern will be obtained using this method.
- **Step 2.** For each of the imputed dataset with monotone missing pattern obtained in Step 1, the remaining missing data will be imputed using the regression method for the monotone pattern with adjustment for covariates including response variable, intervention groups, angioedema at baseline, region, and baseline value of the corresponding endpoint. All available data in the monotone missing pattern data will be used. One imputed dataset will be obtained for each of the imputed dataset at Step 1. So, 40 fully imputed datasets will be obtained altogether.
- **Step 3.** The imputed values in dupilumab group are added by a positive amount d for each imputed data set.
- **Step 4.** The imputed values in placebo group are subtracted by a positive amount p for each imputed data set.
- **Step 5.** Change from baseline in endpoint will be analyzed using ANCOVA model same as the one in primary analysis. Then the SAS MIANALYZE procedure will be used to generate statistical inferences by combining results from the 40 analyses using Rubin's formula.

Step 3 to Step 5 will be repeated iteratively until the p-value for treatment effect of dupilumab compared to placebo estimated in Step 5 is >0.05 .

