| Table 10 - Time window for safety endpoints | 42 |
| Table 11 - Time window for efficacy variables | 43 |
| Table 12 - Time window for pharmacokinetics/pharmacodynamics variables | 43 |
| Table 13 - List of PTs or Medications for CMQs/CDGs | 45 |

VERSION HISTORY

This Statistical Analysis Plan (SAP) only includes the plan for EFC16461 Study C (in omalizumab naïve patients), which is based on the protocol dated 17 March 2022 (amended protocol 5). There are no major changes to the statistical analysis features in this SAP compared to the protocol. Separate SAPs were prepared for Study A and B.

The first participant was randomized on 02 Aug 2022.

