4.6 MULTIPLICITY ISSUES

A multiplicity procedure is proposed to control the overall type-I error rate for testing the primary and selected secondary endpoints. The overall type-I error is controlled at 0.05. The comparisons with placebo will be tested based on the hierarchical order below at 2-sided $\alpha = 0.05$.

1. Change from baseline in ISS7 at Week 24
2. Change from baseline in UAS7 at Week 24
3. Change from baseline in HSS7 at Week 24
4. Proportion of patients with MID (ISS7 ≥ 5) response at Week 24
5. Proportion of patients with UAS7 ≤ 6 at Week 24
6. Proportion of patients with UAS7 = 0 at Week 24
7. Change from baseline in UCT at Week 24

In EU and EU reference countries:

1. Change from baseline in UAS7 at Week 24
2. Change from baseline in ISS7 at Week 24
3. Change from baseline in HSS7 at Week 24
4. Proportion of patients with MID (ISS7 ≥ 5) response at Week 24
5. Proportion of patients with UAS7 ≤ 6 at Week 24
6. Proportion of patients with UAS7 = 0 at Week 24
7. Change from baseline in UCT at Week 24

Study C is considered positive when the primary endpoint (change from baseline in ISS7 at Week 24 in non-EU countries or change from baseline in UAS7 at Week 24 in EU and EU reference countries) achieves statistical significance.

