4.9 INTERIM ANALYSES

No interim analysis is planned.

For Study C, a primary database lock will be performed when all randomized participants in this study have completed their 24-week treatment phase. Analysis will be based on all data collected up to this database lock and will be considered as the final analyses in the Study C CSR.

The database will be updated at the end of the study for all participants to include the post-treatment follow-up information and updates for the events previously ongoing at the time of the primary lock. Additional data between this database lock and last participant completing last visit will be summarized in a CSR addendum.

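### Study C's tipping-point analysis stops at Study B's interim-adjusted significance levels instead of Study C's own 0.05

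*SAP*

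**What the plan says.** Study C SAP, section 4.3.3, sets out a five-step tipping-point analysis for multiply imputed Week 24 values. Imputed dupilumab values are worsened by an amount d, imputed placebo values are improved by an amount p, and the ANCOVA is refitted. Steps 3 to 5 are repeated until the p-value "estimated in Step 5 is >0.021 at IA or >0.043 at final analysis". The section adds that the LS mean difference and "the corresponding p-values will be provided for each combination of shift parameters".

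Elsewhere, the plan gives Study C a single look at 0.05:

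- Study C SAP, section 4.9: "No interim analysis is planned".
- Protocol section 9.5: "No interim analysis is planned for Study A and Study C".
- Study C SAP, section 4.6: "The overall type-I error is controlled at 0.05", with the hierarchy tested at 2-sided 0.05.
- Protocol section 9.4.1: "Study A and Study C are each considered positive when the primary endpoint achieves statistical significance with 2-sided significance level 0.05".

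The Study A SAP, section 4.3.3, ends the same loop when the p-value for "dupilumab compared to placebo estimated in Step 5 is >0.05". The Study B SAP, section 4.3.3, has the same stopping sentence as Study C.

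**The concern.** A tipping point is the shift in the imputed values at which the study's conclusion changes. For Study C that happens when p exceeds 0.05. The written rule uses two other levels. One refers to an analysis that does not exist. The other, 0.043, is stricter than the study's own test, so the loop can end at a shift where Study C would still be positive. A natural reading of the output would take that last cell as the tipping boundary.

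The protocol presents Studies A and C as the two adequate and well-controlled trials supporting the filing. As written, their tipping boundaries would be set at different levels, and no reason is given for the difference.

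**Working it through.** **1. Where 0.021 and 0.043 come from.** Study B SAP, section 4.9, gives two looks, information fraction 0.77 and overall 2-sided alpha 0.05. For a classic O'Brien-Fleming design the critical values are c/√0.77 at the interim and c at the end, with c chosen so that the joint rejection probability under the null is 0.05. This gives nominal levels of 0.0215 and 0.0436. The O'Brien-Fleming-type spending function, applied to each side, gives 0.0213 and 0.0437. Study B's stated 0.021 and 0.043 match, apparently truncated. They have a meaning only for two looks.

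**2. Study C is designed for one look at 0.05.** Protocol section 9.2 gives a difference of 4.23, SD 7.5, 75 per arm, 10% dropout and 2-sided alpha 0.05.

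- Effect size: 4.23/7.5 = 0.564.
- Evaluable per arm: 75 × 0.9 = 67.5.
- Power of the 2-sided t-test at 0.05: 90.2%, against 90% stated.

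The sample size therefore spends the whole 0.05 on one analysis. The alpha in section 2 of the Study C SAP is blacked out, so 0.05 is taken from the protocol and from section 4.6 of that SAP.

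**3. Room before tipping.** Study A's results (Protocol Table 1) serve as an illustration, with a normal approximation and the standard error (SE) held fixed. The critical values are z = 1.960 at 0.05 and z = 2.024 at 0.043. SE = CI width / (2 × 1.960), and room = difference − z × SE.

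| | ISS7 | UAS7 |
|---|---|---|
| Difference (absolute) | 4.23 | 8.53 |
| SE | (6.63 − 1.84)/3.92 = 1.222 | (13.16 − 3.90)/3.92 = 2.362 |
| Room at 0.05 | 4.23 − 2.395 = 1.835 | 8.53 − 4.630 = 3.900 |
| Room at 0.043 | 4.23 − 2.473 = 1.757 | 8.53 − 4.781 = 3.749 |
| Gap | 0.078 (4.2%) | 0.151 (3.9%) |

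**4. In terms of the shift d (ISS7, no placebo shift).** Shifting a fraction m of the dupilumab arm by d moves the mean difference by m × d, so the tipping d is room/m. The documents do not say what share will be multiply imputed rather than handled by worst observation carried forward, so m is assumed.

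- m = 10%: d = 18.4 at 0.05, against 17.6 at 0.043.
- m = 20%: d = 9.2 against 8.8.

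**5. How far the 4% depends on the assumptions.** With Study C's planning values (75 per arm, SD 7.5, difference 4.23) and the variance added by the shift, d at m = 10% is 15.8 against 15.1. The absolute shifts are smaller and the gap is still about 4%. With the same method and an assumed weaker difference of 3.0, d at m = 10% is 5.5 against 4.8, about 13% lower.

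**6. The limiting case.** If the primary p-value falls between 0.043 and 0.05, Study C is positive under section 4.6, yet the stopping criterion in section 4.3.3 is already met with no shift at all.

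**The case against.** The strongest reply is that very little depends on this number. It only ends the iteration of one sensitivity analysis. Whether Study C is positive is decided in section 4.6 at 0.05, and section 4.3.3 attaches no decision to the stopping cell. The error runs in the conservative direction. The p-value is reported for every shift combination, so a reader can judge the results directly. The other missing-data sensitivity analysis in the same section, copy increment from placebo, uses no threshold. All of this stands and is why the consequence is limited. It does not fully repair the rule, because the loop may stop before p reaches 0.05, and the true boundary then need not appear in the output.

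The illustration also has limits. The fixed-SE values of d are at the upper end. ISS7 runs from 0 to 21. With a mean dupilumab change of −10.24 in Study A, adding 17.6 gives a change of +7.36, which keeps the mean Week 24 score within 21 only if mean baseline is at most about 13.6 (21 − 7.36). That assumes imputed participants resemble the arm average, and the documents give no baseline mean. In the 10% scenario both boundaries may therefore lie near or beyond the scale limit. The step size for d and p is not stated, so in practice the two levels may differ by a single step.

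Finally, the Study C SAP's Version History says "There are no major changes to the statistical analysis features in this SAP compared to the protocol". That offers no support for 0.043, but it is weak evidence against it, because the protocol leaves sensitivity details to the SAP and sets no tipping threshold. The contradiction rests on sections 4.3.3, 4.6 and 4.9 of the Study C SAP.

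**Conclusion.** The stopping rule is wrong as written. It contradicts Study C's own single-look design, and nothing in the protocol or SAP justifies 0.043 for this study. Carry-over from the Study B SAP is the likely explanation. Two other Study B phrases also appear in the Study C SAP but not in the matching Study A sections: the restriction to the final analysis in section 4.5.1, and the reference in section 4.3.4 to visits not reached by the cutoff date.

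The effect is to understate robustness, never to overstate it. The shortfall is about 4% of the room before tipping if Study C behaves like Study A, and more if the effect is weaker. These sizes rest on Study A's estimates or Study C's planning values. The d figures also rest on assumed imputed shares.

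**What to change.** In section 4.3.3 of the Study C SAP, end the iteration of Steps 3 to 5 when the Step 5 p-value exceeds 0.05, using the wording of the Study A SAP, and delete the mention of an interim analysis. The cost is one sentence in the SAP and one constant in the program. The correction should be made before unblinding, so that it is not a post hoc change to a prespecified rule.

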4.3.4 Supplementary analyses

The following supplementary analysis will be performed:

As-observed analysis (Including all data after taking selected prohibited and/or rescue medications)

The data collected after taking the select prohibited medications and/or rescue medications will be included in the sensitivity analysis to evaluate the robustness of the primary analysis results with respect to the intercurrent event handling strategy while taking selected prohibited medications and/or rescue medications. (eg, treatment policy strategy). For missing data, a multiple imputation approach will be used to impute missing Week 24 value, and this multiple imputation will use all participants.

Worst possible score

For participants taking selected prohibited and/or rescue medications (see [Table 4](#)), their data after the medication start date will be excluded from the analysis, and the worst possible score (ie, 21 for ISS7 and 42 for UAS7) will be assigned to the Week 24 value. In case there is missing data, a multiple imputation approach will be used to impute missing Week 24 value, and this multiple imputation will use all participants excluding participants who have taken the selected prohibited medications and/or rescue medications on or before Week 24.

Each of the imputed complete data will be analyzed by fitting an analysis of covariance (ANCOVA) model with the baseline value of the primary endpoint, intervention group, presence of angioedema at baseline, and region as covariates. Statistical inference obtained from all imputed data will be combined using Rubin's rule. Descriptive statistics including number of participants, mean, standard error, and least squares (LS) mean changes (and standard error) score will be provided. In addition, difference of the dupilumab group against placebo in LS means and the corresponding 95% confidence intervals (CI) will be provided along with the p-values.

The change from baseline and percent change from baseline will be summarized and analyzed by week using the same approach as the primary endpoint. Descriptive statistics including number of participants, mean, standard error, and least squares (LS) means will be provided. In addition, difference in LS means and the corresponding 95% confidence intervals (CI) will be provided along with the p-values. Figures over time will also be presented. In addition, descriptive summaries by week up to Week 36 and figures over time will be provided using the ITT population, while WOCF/MI and other imputation approach will not impute visits a participant would not have reached by the cutoff date.

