VERSION HISTORY

This Statistical Analysis Plan (SAP) only includes the plan for EFC16461 Study A (in omalizumab naïve patients), which is based on the protocol dated 29 April 2021 (amended protocol 4). A separate SAP is prepared for Study B. This section summarizes the major changes to the SAP.

The first participant was randomized on 06 February 2020.

Table 1 - Major changes in statistical analysis plan

| SAP Version | Approval Date | Changes | Rationale |
|-------------|---------------|---|---|
| 1 | 14-Jan-2021 | Not Applicable | Original version |
| 2 | 16-Jun-2021 | 
Sensitivity analysis adding a delta to the WOCF values added.
 
Supplementary analysis using a worst possible score added.
 
Added blinded medical review to confirm the medications/procedures that are considered as treatment failure.
 
Added summaries and analysis of cumulative number of itch and/or hive-free days.
 
Replaced additional analysis of proportion of angioedema-free days from Week 4-12 and 13-24 with cumulative number of angioedema-free days from Week 4-12, 13-24 and 4-24 in all participants and participants with angioedema at baseline.
 
Added exposure adjusted AE summaries with risk differences and hazard ratios to select AE summaries.
 
Added “Keratitis FDA” to other AE groupings.
 | 
To check robustness by applying worse scores than WOCF.
 
An analysis using worst possible score was requested by the US FDA.
 
Per FDA recommendation to define the intercurrent event for those medications/procedures considered treatment failure
 
This additional analysis adds value to provide a total summary over the entire planned treatment period
 
For consistency with above additional analysis
 
Per FDA recommendation
 
For consistency with other dupilumab studies
 |

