| | Change from baseline in UAS7 at Week 24 (EU and EU reference countries) | | 
 Discontinuing the study intervention (but not taking selected prohibited and/or rescue medications^b prior to Week 24): all data collected after discontinuation will be used in the analysis (treatment policy strategy). Taking selected prohibited medications and/or rescue medications^b prior to Week 24: data will be excluded after the medication usage, and the participant's worst post-baseline value on or before the time of the medication usage will be assigned to the Week 24 value (for participants whose post-baseline values are all missing, the participant's baseline value will be used for the Week 24 value) (composite strategy) 
After applying the rules for intercurrent events, if there is still missing data, then the missing data imputation rules are as follows:
 
 After study intervention discontinuation due to lack of efficacy prior to Week 24: WOCF approach (as described above) will be used to impute missing data if needed. After study intervention discontinuation due to reasons other than lack of efficacy prior to Week 24: multiple imputation (MI) approach will be used to impute missing Week 24 value, and this multiple imputation will use all participants excluding participants who have taken the selected prohibited medications and/or rescue medications prior to Week 24 and excluding participants who discontinue study intervention due to lack of efficacy prior to Week 24. | | |

| Endpoint Category | Estimands | | | |
|---|---|------------|---|---|
| | Endpoint(s) ^a | Population | Intercurrent event(s) handling strategy and missing data handling | Population-level summary |
| Secondary objective: To demonstrate the efficacy of dupilumab on urticaria activity composite endpoint and itch or hives, separately, at various time points | | | | |

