The primary efficacy endpoints will be analyzed using an analysis of covariance (ANCOVA) model with the baseline value of the primary endpoint, intervention group, presence of angioedema at baseline, and region as covariates, with intercurrent events and missing data being handled by a hybrid method of the worst-observation carried forward (WOCF) and multiple imputation. For participants taking selected prohibited medications and/or rescue medications (see [Table 4](#)), their data after the medication start date will be excluded, and the worst postbaseline value on or before the time of the medication usage will be assigned to the Week 24 value (for participants whose postbaseline values are all missing, the baseline will be used). Participants who discontinue the intervention prematurely are encouraged to follow the planned clinical visits and in these participants who did not take the selected prohibited medications and/or rescue medications, all data collected after intervention discontinuation will be used in the analysis. For these participants, missing data may still happen despite all efforts to collect the data after intervention discontinuation. For participants who discontinue study intervention due to lack of efficacy, all data collected after discontinuation will be used in the analysis, and a WOCF approach will be used to impute missing Week 24 value if needed (ie due to study discontinuation). For participants who discontinued study intervention for reasons other than lack of efficacy, a multiple imputation approach will be used to impute the missing Week 24 value. This multiple imputation will include all participants except participants who have taken the selected prohibited medications and/or rescue medications on or before Week 24 and will also exclude participants who discontinued study intervention due to lack of efficacy on or before Week 24.

Each of the imputed complete data will be analyzed by fitting an ANCOVA model as described above. Statistical inference obtained from all imputed data will be combined using Rubin's rule. Descriptive statistics including number of participants, mean, standard error, and least squares (LS) mean changes (and standard error) score will be provided. In addition, difference of the dupilumab group against placebo in LS means and the corresponding 95% confidence intervals (CI) will be provided along with the p-values.

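### Study C's worst-possible-score and as-observed analyses change the lack-of-efficacy rule as well as the rescue rule, so a difference from the primary cannot be attributed to rescue handling alone

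*SAP*

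**What the plan says.** **Primary analysis (Study C SAP 1.2.1 and 4.3.2).** Taking a selected prohibited or rescue medication is an intercurrent event handled by WOCF. Stopping study drug for lack of efficacy falls under a missing-data rule. Data collected after stopping are used, and if Week 24 is still missing, a "WOCF approach (as described above) will be used to impute missing data if needed". The MI that fills other gaps leaves out rescue takers and "will also exclude participants who discontinued study intervention due to lack of efficacy on or before Week 24".

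**Sensitivity analyses (4.3.3).** The copy-increment-from-placebo model and the tipping-point analysis for missing data both apply WOCF to lack-of-efficacy discontinuers first, with a reference back to the primary.

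**Supplementary analyses (4.3.4).**
- Worst possible score: for rescue takers, "the worst possible score (ie, 21 for ISS7 and 42 for UAS7) will be assigned to the Week 24 value". Any other participant without a Week 24 score goes to MI. On who informs that model, the section says only that "this multiple imputation will use all participants excluding participants who have taken the selected prohibited medications and/or rescue medications on or before Week 24".
- As-observed: data after rescue are used. "For missing data, a multiple imputation approach will be used to impute missing Week 24 value, and this multiple imputation will use all participants". Its stated purpose is to test robustness to the rescue-handling strategy.

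Neither supplementary analysis mentions lack of efficacy. The Study A and B SAPs word the imputation in 4.3.4 the same way, but their 4.3.3 also lists a tipping-point analysis on the WOCF values, which pushes them towards 21 (ISS7) or 42 (UAS7). Study C's 4.3.3 does not list it.

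**The concern.** The affected participant stopped for lack of efficacy, took no selected medication and has no Week 24 score. The primary and both 4.3.3 analyses hold that person at the worst value seen. Both 4.3.4 analyses instead predict a Week 24 value under missing at random. They also let lack-of-efficacy discontinuers inform the prediction for others.

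Two things are at stake.

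- **Attribution.** A supplementary analysis should differ from the primary in one respect, so that a difference can be read. Here rescue handling and lack-of-efficacy handling move together, although the as-observed analysis says it examines only the former.
- **Coverage.** Without the WOCF tipping point, no listed Study C analysis has a rule that scores these leavers worse than WOCF. The analysis named for the worst score treats them, on average, more leniently than the primary.

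**Working it through.** **1. The rules side by side (Study C SAP)**

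| Analysis | Rescue takers | Lack-of-efficacy leaver, no rescue, Week 24 missing | Lack-of-efficacy discontinuers in MI model? |
|---|---|---|---|
| Primary (1.2.1, 4.3.2) | WOCF | WOCF | No |
| Both 4.3.3 analyses | WOCF | WOCF | Leavers already filled by WOCF |
| Worst possible score (4.3.4) | 21 / 42 | MI | Yes, unless they took rescue |
| As-observed (4.3.4) | Observed data, else MI | MI | Yes |

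Moving from the primary to either 4.3.4 row changes the second column, as intended, and also the third and fourth.

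**2. The plan's own figure**

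Inputs from protocol 9.2: difference 4.23, SD 7.5, two-sided alpha 0.05, power 90%, dropout 10%. The effect size is 4.23/7.5 = 0.564. By the normal formula, n = 2 × (1.960 + 1.282)² / 0.564² ≈ 66.1, so 67 per arm. Then 67/0.90 = 74.4, so 75. The noncentral-t power at 67 per arm is 0.900. The stated 75 per group and 90% reproduce, and nothing below alters them.

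**3. Gap between WOCF and MI for one leaver**

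The documents do not give this, so it was simulated under assumptions:
- weekly ISS7 with baseline mean 16 and SD 3, limited to 8–21 (assumed);
- Week 24 mean changes of −6.01 and −10.24 (Study A, protocol Table 1) and SD 7.5;
- a leaver is anyone improved by less than 2 points at the stopping week (assumed);
- Week 24 is predicted from baseline and the participant's own weekly scores, in line with the MI code in the Study A and B SAPs, Appendix 5.

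| Stopping week | Placebo: WOCF / MI / gap | Dupilumab: WOCF / MI / gap |
|---|---|---|
| 8 | 19.0 / 13.8 / 5.2 | 19.1 / 11.6 / 7.5 |
| 12 | 19.3 / 14.3 / 5.0 | 19.2 / 12.4 / 6.9 |
| 16 | 19.5 / 14.8 / 4.7 | 19.4 / 13.1 / 6.2 |

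Gaps come from unrounded means. Single imputed draws exceeded WOCF in 6–16% of cases; the predicted mean essentially never did.

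**4. Effect per leaver on an arm mean of 75**

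- Placebo: 4.7/75 = 0.063 to 5.2/75 = 0.069.
- Dupilumab: 6.2/75 = 0.083 to 7.5/75 = 0.100.

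**5. Effect on the treatment difference**

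The shift in (dupilumab − placebo) is (kP × gP − kD × gD)/75, where k is the number of leavers and g the gap. With the Week 12 gaps and illustrative counts:

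- two per arm: (10.0 − 13.8)/75 = −0.05, slightly wider;
- three placebo, one dupilumab: (15.0 − 6.9)/75 = +0.11, narrower;
- one placebo, three dupilumab: (5.0 − 20.7)/75 = −0.21, wider.

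A cruder grid assumes a common gap of 2–6 points and leaver fractions of 2–8% (placebo) and 2–5% (dupilumab). It moves −4.23 to between −4.23 − 6 × (0.05 − 0.02) = −4.41 and −4.23 + 6 × (0.08 − 0.02) = −3.87. For scale, the standard error of the difference is about 7.5 × √(2/75) = 1.22.

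**The case against.** The strongest reply is that 4.3.4 is meant to vary rescue handling. Lack-of-efficacy discontinuation is a missing-data rule in the estimand table, so using MI for all remaining gaps is a coherent choice. That is fair as a design option. It does not answer the attribution problem, because the primary does not use MI for these people.

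The affected group is also narrow. Lack-of-efficacy stoppers who took rescue do get 21 or 42. Follow-up after stopping is encouraged and used, and four of seven diary days make a valid week. Planned dropout for all causes is 10%, about 7 or 8 per arm, so several such leavers in one arm would be a large share of it. Both analyses sit outside the testing hierarchy in 4.6. All of this stands and keeps the point small.

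A reader might infer four stronger things that the documents do not support:

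- **That leavers are scored at the arm average.** This would give 10.2/75 = 0.136 and 6.0/75 = 0.080 points each if WOCF meant no change from baseline. The Study A and B code conditions on each participant's own weekly changes, and Study C describes the same two steps, so the arm mean overstates the gap.
- **That the rule favours dupilumab.** MI helps whichever arm loses more such participants. An excess on placebo narrows the difference.
- **That these leavers ought to receive 21 or 42.** The Study A version history says "An analysis using worst possible score was requested by the US FDA", but not how lack-of-efficacy leavers were to be treated. That assignment would also change two rules relative to the primary.
- **That every imputed value is better than WOCF.** This holds on average, not draw by draw.

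**Conclusion.** The mismatch is in the text and worth correcting, as a matter of interpretability. Both 4.3.4 analyses alter lack-of-efficacy handling alongside rescue handling and, on average, score the affected leavers better than the primary does. Study C has no listed analysis that takes them below WOCF by rule.

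The likely size is about 0.06 to 0.07 ISS7 points per placebo leaver and 0.08 to 0.10 per dupilumab leaver at 75 per arm, against a planned difference of 4.23. This rests on the assumed trajectories and on the supplementary MI following the method described for the primary. The number of leavers is not in the documents, so neither the total nor its sign can be stated. The primary result, the power and the type I error are unaffected.

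**What to change.** In Study C SAP 4.3.4, add to both the worst-possible-score and the as-observed analyses that participants who discontinued study intervention for lack of efficacy and have no Week 24 value receive WOCF as in the primary. Also exclude lack-of-efficacy discontinuers from the MI model. Only rescue handling then differs from the primary.

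The cost is a sentence in each analysis and a few lines of code before database lock, with no effect on sample size or data collection. The supplementary estimate may become slightly less favourable. This change restores attribution but does not by itself stress these leavers beyond WOCF. The absence of the WOCF tipping point is a separate choice for the sponsor.
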